## **6.6. Intervention After the End of the Trial**

There will be no provision of darigabat for participants after they complete or discontinue treatment in this trial.

Participants who complete through the 14-week Treatment Period of the trial may have the opportunity to receive post-trial supportive therapy offered via the sponsor. Additional details are provided in the Operations Manual.

## **6.7. Prior and Concomitant Therapy**

### **6.7.1. Time Period for Recording Prior and Concomitant Therapy**

The investigator will record all therapies (including vaccines, over-the-counter or prescription medicines, vitamins, and/or herbal supplements) taken by the participant from 30 days prior to signing the ICF through the end of the evaluation period (defined as the time period during which participants are evaluated for primary and/or secondary objectives).

For concomitant medications, the following information will be recorded in the eCRF: medication, indication, dose, frequency, route, start date, and end date. For nondrug therapies or procedures, the following information will be recorded in the eCRF: therapy/procedure name, indication, start date, and end date.

The medical monitor should be contacted if there are any questions regarding concomitant or prior therapy.

### **6.7.2. Prohibited Therapy**

Participants are required to discontinue use of prohibited medications in accordance with predefined washout periods, as shown in [Table 5](#).

**Table 5: Prohibited Prior Medications**

Prohibited Prior Medications	Washouta (if applicable)
Moderate or strong inducers of CYP3A4 metabolism (see Section 10.7 )	5 weeks
Moderate or strong inhibitors of CYP3A4, including Paxlovid (see Section 10.7 )	14 days or 5 half-lives, whichever is longer
P-gp substrates with a narrow therapeutic index (eg, digoxin, dabigatran)	14 days
BCRP substrate rosuvastatin	5 days
All psychoactive substances other than antidepressants (unless otherwise noted) including but not limited to: 
 
• Opiates
 
• Anxiolytics (eg, benzodiazepines, non-benzodiazepine anxiolytics)
 
• Beta receptor antagonists used for any indication
 
• Antiseizure/neuropathic pain medications used for any indication (eg, gabapentin, pregabalin, topiramate, phenytoin, phenobarbital)
 
• Hypnotics 
 
○ Sleep medications (eg, zolpidem, zaleplon, eszopiclone, trazodone, and suvorexant or other orexin receptor antagonists) are permitted if medically prescribed at doses labeled for insomnia and used no more than 3 times per week
 
 
 
• Mood stabilizers (eg, lithium, divalproex, carbamazepine, lamotrigine)
 
• Stimulants (eg, amphetamine, methylphenidate, modafinil)
 
• Antipsychotics
 
	14 days
Antidepressants	14 days, except for fluoxetine and Symbyax, which require a washout of 28 days
D2/3 agonist (eg, pramipexole)	14 days or 5 half-lives, whichever is longer
Any investigational agent	60 days

Abbreviations: BCRP=breast cancer resistance protein; CYP=cytochrome P450; D2/3=dopamine D2/D3 receptor agonist; ICF=informed consent form; P-gp=P-glycoprotein.

a The required washout duration is based on the period prior to the Baseline Visit. Once the participant signs the ICF, the participant has up to 28 days prior to the Baseline Visit to washout. If the participant happened to washout prior to the Screening Visit for their own reasons and out of their own will, this is acceptable and must be documented in the medical records. Following consultation with the medical monitor, the Screening Period may be extended if needed to accommodate a washout duration that is longer than 28 days.

The concomitant medications that are prohibited during the trial are listed in [Table 6](#).

The medical monitor should be contacted regarding the appropriateness of a participant's continued participation in the trial in the event that initiation of therapy with a prohibited

concomitant medication is deemed necessary, in the investigator's opinion, for the treatment of a TEAE.

The medical monitor should be contacted if a participant tests positive for cannabis products/THC during the trial to determine whether participation in the trial should continue.

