- p Reflex viral hepatitis C PCR testing if hepatitis C antibody is positive or indeterminate.
- q A confirmatory FSH is required for all postmenopausal women.
- r With participants maintaining their normal BID dosing routine, a single daytime blood sample for determination of plasma darigabat concentration will be collected at Visits 3, 4, 5, and 6. The date and time of the PK sample, as well as the time of ingestion of previous dose of IMP, will be recorded in the source documentation.
- s Future biospecimen research sample is optional and is only to be collected if signed consent is obtained from the participant. Sample can be collected at any time following confirmation of participant eligibility and prior to initiation of first dose.
- t Randomization will occur at Baseline and IMP will be dispensed after randomization. Participants will start taking IMP on Day 1 (eg, the day following their Baseline Visit). Dosing will continue through Visit 6 (Day 98) or ET.

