#### 4.1.2. Treatment Period

Participants will initiate outpatient dosing beginning on Day 1 (the day after the Baseline Visit). During the 2-week Titration Period, the participant's dose will be increased in a blinded fashion up to the randomized dose level (darigabat 25 mg BID or placebo BID). In the darigabat 25 mg BID group, darigabat will be administered as 5 mg BID for 1 week followed by 12.5 mg BID for another week during the Titration Period, and then 25 mg BID during the 12-week Maintenance Treatment Period. A summary of the dosing schedule is provided in [Table 3](#).

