11.	
Participants with any of the following abnormalities in clinical laboratory tests at the Screening Visit, as assessed by the central laboratory and confirmed by a single repeat measurement, if deemed necessary:
 
 
• AST or ALT <math>\geq 2 \times</math> ULN
 
• Total bilirubin <math>\geq 1.5 \times</math> ULN. If Gilbert's syndrome is suspected, total bilirubin <math>>1.5 \times</math> ULN is acceptable if the conjugated or direct bilirubin fraction is <math><20\%</math> of total bilirubin
 
• eGFR <math><60</math> mL/min/1.73 m^2 (as estimated by the CKD-EPI 2021 equation [Levey et al, 2009; Delgado et al, 2022]) and as reported by the central laboratory
 
• TSH <math><</math> LLN
 
• Hemoglobin <math><</math> LLN
 
• WBC count <math><</math> LLN or <math>></math>ULN
 
• Neutrophil count <math><</math> LLN or <math>></math>ULN
 
• Platelet count <math><</math> LLN or <math>></math>ULN
 

12.	
Any other abnormal safety findings unless, based on the investigator's judgment, the findings are not medically significant and would not impact the safety of the participant or the interpretation of the trial results. The medical monitor should be contacted to discuss individual cases, as needed.
 
Tests with abnormal results that are potentially exclusionary should be repeated to ensure reproducibility of the result before excluding a potential participant based on criteria provided in the protocol.

Prior or Concomitant Therapies	
13.	Use of prohibited medications prior to randomization within the required wash-out period or likely to require prohibited concomitant therapy during the trial (see Section 6.7 ).
Other	
14.	Female participants who are breastfeeding or who have a positive pregnancy test result prior to receiving IMP.
15.	
Any condition possibly affecting drug absorption, including bowel resections, bariatric weight loss surgery, or gastrectomy (this does not include gastric banding).
 
Considering or scheduled to undergo any surgical procedure during the trial.

16.	Any other condition that would preclude IMP administration (eg, difficulty swallowing) or trial participation (eg, poor venous access).
17.	Participants who are known to be allergic or hypersensitive to the IMP or any of its components.

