**Table 6: Prohibited Concomitant Medications and/or Therapies**

Prohibited Concomitant Medications/Therapies During Trial Conduct

All psychoactive substances (unless otherwise noted) including but not limited to:
 
 
• Antidepressants
 
• Opiates
 
• Anxiolytics (eg, benzodiazepines, non-benzodiazepine anxiolytics)
 
• Beta receptor antagonists used for any indication
 
• Antiseizure/neuropathic pain medications used for any indication (eg, gabapentin, pregabalin, topiramate, phenytoin, phenobarbital)
 
• All first-generation antihistamines are prohibited for all indications, except for diphenhydramine, which is permitted only if medically indicated for insomnia and used no more than 3 times per week.
 
• Hypnotics 
 
○ Sleep medications (eg, zolpidem, zaleplon, eszopiclone, trazodone, and suvorexant or other orexin receptor antagonists) are permitted if medically prescribed at doses labeled for insomnia and used no more than 3 times per week
 
 
 
• Mood stabilizers (eg, lithium, divalproex, carbamazepine, lamotrigine)
 
• Stimulants (eg, amphetamine, methylphenidate, modafinil)
 
• Antipsychotics
 

D2/3 agonists (eg, pramipexole)
Any OTC treatments for the treatment of panic disorder or anxiety disorder(s) (eg, cannabis products/THC, CBD a , herbal supplements, including but not limited to valerian root, St. John's wort, and GABA supplements)
Investigational agents
Any drug or product that is a moderate to strong inducer of CYP3A4 metabolism, which has the potential to lower darigabat exposure levels. An example list of strong (>80% reduction in AUC) and moderate (50% to 80% reduction in AUC) inducers is provided in Section 10.7 .
Any drug or product that is classified as a significant (ie, strong or moderate) inhibitor of the CYP3A4 metabolic pathway, which has the potential to increase darigabat exposure levels. An example list of strong (eg, >5-fold increase in AUC) and moderate (eg, 2-to 5-fold increase in AUC) inhibitors is provided in Section 10.7 .
BCRP substrate rosuvastatin
Exposure-based therapy
Systemic steroids are prohibited. Any steroid that is not systemic (eg, topical or inhaled) is permitted.

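### Narrow-therapeutic-index P-gp substrates must be washed out before Baseline, but the list of drugs prohibited during the trial omits them

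*Protocol*

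**What the plan says.** Section 6.7.2 of the protocol uses two tables. Table 5 covers prior medications and gives each a washout. One row reads "P-gp substrates with a narrow therapeutic index (eg, digoxin, dabigatran"), with 14 days in the washout column. Footnote a fixes the reference point: "The required washout duration is based on the period prior to the Baseline Visit".

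After Table 5 the text turns to the treatment period: "The concomitant medications that are prohibited during the trial are listed in" Table 6. Table 6 contains no P-gp entry, whereas the other transporter-substrate row of Table 5, "BCRP substrate rosuvastatin", is repeated there.

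On timing, Section 4.1.2 states: "Participants will initiate outpatient dosing beginning on Day 1 (the day after the Baseline Visit"). Footnote t of the Schedule of Assessments adds: "Dosing will continue through Visit 6 (Day 98) or ET".

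Two other rules use the idea of a prohibited concomitant treatment. The second part of Exclusion Criterion 13 (Section 5.2) removes people who are "likely to require prohibited concomitant therapy during the trial". Section 6.7.2 also requires the medical monitor to be consulted about "continued participation in the trial in the event that initiation of therapy with a prohibited" concomitant drug is judged necessary to treat a treatment-emergent adverse event.

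**The concern.** A washout before the first dose makes sense for an interacting drug if that drug also stays away while the investigational product is being taken. Here the restriction stops on the day before dosing begins. Read literally, a participant could stop digoxin for 14 days, be randomized, and resume it on Day 1, or could be started on dabigatran in Week 6, without breaching any stated rule.

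The two linked safeguards depend on the same list. If the class is not a prohibited concomitant medication, a likely future need for it does not clearly meet Exclusion Criterion 13, and starting it for an adverse event does not trigger the mandatory call to the medical monitor. Exclusion Criterion 3 also tolerates conditions that are well controlled on non-prohibited concomitant medication, which on the Table 6 wording would include a P-gp substrate.

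The stake is participant safety. The sponsor itself singled out the class and described it by its narrow therapeutic index. The primary and key secondary analyses are not touched.

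**Working it through.** No alpha, power or effect size enters. The check is a row-by-row comparison of the two tables, followed by a search for any other rule.

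**Step 1. Compare the rows.**

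| Table 5 class | Counterpart in Table 6 |
|---|---|
| Moderate or strong CYP3A4 inducers | Yes |
| Moderate or strong CYP3A4 inhibitors | Yes |
| Narrow-therapeutic-index P-gp substrates | **No** |
| Rosuvastatin | Yes |
| Psychoactive substances | Yes |
| Antidepressants | Yes (bullet under psychoactive substances) |
| D2/3 agonists | Yes |
| Investigational agents | Yes |

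Result: 8 rows, 7 carried over, 8 − 7 = 1 not carried over.

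**Step 2. Rule out a row lost in reading the PDF.** The abbreviation list under Table 5 defines P-gp. The list under Table 6 defines BCRP and CYP but not P-gp. This agrees with the row being absent from the source.

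**Step 3. Count the days covered.** The 14 washout days precede the Baseline Visit (Day −1), when no study drug is taken. Planned dosing runs from Day 1 to Day 98: 98 − 1 + 1 = 98 days. Days under an explicit P-gp restriction: 0 of 98. This is the missing row expressed in time, not a separate finding.

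**Step 4. Look for a rule elsewhere.** Section 10.7 lists only CYP3A4 inducers and inhibitors. The notes to Table 6 do not mention the class. Neither amendment summary (Version 3.0 at the front of the protocol, Version 2.0 in Section 10.9) records a deliberate removal or a reason to treat the class differently. The SAP does not address it. Section 6.7.1 invites sites to contact the medical monitor with questions, which is not a prohibition.

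**The case against.** The strongest reply accepts the missing row and disputes its weight.

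- **Exclusion Criterion 13 cites Section 6.7 as a whole, not Table 6.** The lead-in to Table 5 calls its contents prohibited medications, so a site could read a likely digoxin user as ineligible. The first part of the criterion also stops a current user from being randomized without a washout. The second point stands. The first is a possible reading, but the criterion speaks of concomitant therapy during the trial, which closely follows the sentence pointing to Table 6.
- **No sensible site would restart the drug on Day 1.** Probably true, and a new start during treatment is the more realistic case. The text still bars neither.
- **Other safeguards exist.** Exclusion Criteria 3 and 9 remove many likely users. A significant on-treatment ECG abnormality calls for a repeat ECG and discussion with the medical monitor (Section 8.2.4). Immediate safety concerns go to the medical monitor (Section 8), and serious events are reported within 24 hours (Section 8.3.1). These shrink the gap. They are entry, consultation or reporting steps, and none bars the class.
- **The tables need not mirror each other.** Table 6 has entries with no row of their own in Table 5, such as exposure-based therapy. That is fair, but a drug restricted only during the treatment period is easier to understand than one restricted only before it.
- **No hazard is shown, and the study is closing.** Both are correct. They limit the consequence and the remedy, but do not fill the gap in the rule.

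**Conclusion.** The concern holds as a textual gap in a safety rule. One of eight Table 5 classes has no on-treatment counterpart, and no other provision supplies one, so the explicit restriction covers none of the 98 planned dosing days. The two tables do not strictly contradict each other; a single row is missing.

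The practical consequence is small. The number of participants affected is not given and is likely to be few or none. Whether taking these drugs with darigabat 25 mg BID matters clinically cannot be judged from the documents. Efficacy estimates, error rates and power are unaffected. The conclusion rests on reading Table 6 as the governing list during treatment, as Section 6.7.2 says it is. The omission looks inadvertent, but that is an inference from the absence of any stated reason.

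The row should be corrected, without treating the matter as a threat to the trial's conclusions.

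**What to change.** Add the P-gp substrate class to Table 6 in the same words as Table 5, next to the rosuvastatin row. Exclusion Criterion 13 and the medical-monitor trigger then apply without further edits. An equivalent is one sentence stating that every Table 5 class stays prohibited through the last dose.

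The cost is one row, and possibly a few more exclusions or calls to the medical monitor. The sponsor has made this kind of repair before: systemic steroids were added to Table 6 in Version 3.0 and beta receptor antagonists to Table 5 in Version 2.0, each described as an inadvertent omission.

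SAP Section 1 reports the February 2025 decision to close the study, so the row mainly matters if dosing continues or the text is reused. For data already collected, use the concomitant medication listing in SAP Section 5.17.2 to flag on-treatment use of these drugs descriptively when interpreting safety. Do not reclassify such use as a protocol deviation, because the protocol did not prohibit it.

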**Table 6: Prohibited Concomitant Medications and/or Therapies**

Prohibited Concomitant Medications/Therapies During Trial Conduct

All psychoactive substances (unless otherwise noted) including but not limited to:
 
 
• Antidepressants
 
• Opiates
 
• Anxiolytics (eg, benzodiazepines, non-benzodiazepine anxiolytics)
 
• Beta receptor antagonists used for any indication
 
• Antiseizure/neuropathic pain medications used for any indication (eg, gabapentin, pregabalin, topiramate, phenytoin, phenobarbital)
 
• All first-generation antihistamines are prohibited for all indications, except for diphenhydramine, which is permitted only if medically indicated for insomnia and used no more than 3 times per week.
 
• Hypnotics 
 
○ Sleep medications (eg, zolpidem, zaleplon, eszopiclone, trazodone, and suvorexant or other orexin receptor antagonists) are permitted if medically prescribed at doses labeled for insomnia and used no more than 3 times per week
 
 
 
• Mood stabilizers (eg, lithium, divalproex, carbamazepine, lamotrigine)
 
• Stimulants (eg, amphetamine, methylphenidate, modafinil)
 
• Antipsychotics
 

D2/3 agonists (eg, pramipexole)
Any OTC treatments for the treatment of panic disorder or anxiety disorder(s) (eg, cannabis products/THC, CBD a , herbal supplements, including but not limited to valerian root, St. John's wort, and GABA supplements)
Investigational agents
Any drug or product that is a moderate to strong inducer of CYP3A4 metabolism, which has the potential to lower darigabat exposure levels. An example list of strong (>80% reduction in AUC) and moderate (50% to 80% reduction in AUC) inducers is provided in Section 10.7 .
Any drug or product that is classified as a significant (ie, strong or moderate) inhibitor of the CYP3A4 metabolic pathway, which has the potential to increase darigabat exposure levels. An example list of strong (eg, >5-fold increase in AUC) and moderate (eg, 2-to 5-fold increase in AUC) inhibitors is provided in Section 10.7 .
BCRP substrate rosuvastatin
Exposure-based therapy
Systemic steroids are prohibited. Any steroid that is not systemic (eg, topical or inhaled) is permitted.

Abbreviations: AUC=area under the concentration-time curve; BCRP=breast cancer resistance protein; CBD=cannabidiol; CYP=cytochrome P450; D2/3=dopamine D2/D3 receptor agonist; eCRF=electronic case report form; GABA=gamma-aminobutyric acid; IMP=investigational medicinal product; OTC=over-the-counter; THC=tetrahydrocannabinol.

Note: In the event that rescue therapy with a benzodiazepine is required at the discretion of the investigator, the medical monitor should be contacted to determine whether the participant remains eligible to continue participation in the trial.

Note: Non-benzodiazepine sleep aids (eg, zolpidem, zaleplon, eszopiclone, trazodone, and suvorexant or other orexin receptor antagonists) are permitted for the treatment of insomnia, but not within 10 hours of administration of IMP, regardless of indication. For the non-benzodiazepine sleep aids, site personnel should utilize one of the listed medications that are approved for this indication and the specific prescribing information should be used to determine the maximum allowable daily dose for the treatment of insomnia. Non-benzodiazepine sleep aids must not be administered within 12 hours prior to scheduled efficacy scale and safety assessments. Investigators are encouraged to delay scale administration until 12 hours have elapsed, if at all possible. However, if delaying the administration of efficacy and safety scales is not feasible, the scales should still be administered and the use of the sleep aid documented, including a notation of the drug name, dose, and time of administration on the eCRF.

a Topical CBD (eg, oil or lotion) used for muscle spasms or massages will be evaluated upon discussion with the medical monitor.

## **7. DISCONTINUATION OF TRIAL INTERVENTION AND PARTICIPANT DISCONTINUATION/WITHDRAWAL**

Details on discontinuation of individual trial sites or of the trial as a whole are provided in [Section 10.1.8](#).

### **7.1. Discontinuation of Trial Intervention**

For QTcF, liver enzymes, and/or hematological abnormalities meeting AESI criteria as described in [Section 8.3.7](#), a repeat evaluation should be immediately performed for confirmation and the medical monitor notified.

If the repeat evaluation is confirmed abnormal, the treatment with study drug should be discontinued and the early termination visit should be completed.

If a participant permanently discontinues IMP, refer to the Schedule of Assessments ([Section 1.3](#)) for data to be collected following IMP discontinuation.

If a participant discontinues IMP due to an AE, the investigator or other trial personnel will make every effort to follow the event until it has resolved or stabilized.

### **7.2. Participant Discontinuation/Withdrawal From the Trial**

All participants have the right to withdraw from the trial at any time without prejudice. Participants cannot withdraw consent for use of data already collected as part of the trial, but can withdraw consent for future participation. The investigator can also discontinue a participant from the trial at any time for safety, behavioral, or compliance reasons. Unless a participant provides written withdrawal of consent or there is other written documentation by the investigator confirming the participant's verbal intent to completely withdraw from the trial, participants should be followed for all protocol-specified evaluations and assessments, if possible.

At the time of discontinuation from the trial, if possible, an early termination visit should be conducted. Unless a participant withdraws consent, an Early Termination Visit and end of trial procedures should be conducted if a participant discontinues IMP. Unless clinically necessary, the initiation of any prohibited medications should occur after the completion of all of the assessments at the Early Termination Visit and Telephone Visits 7 and 8. See the Schedule of Assessments ([Section 1.3](#)) for data to be collected at the time of discontinuation and follow-up and for any further evaluations that need to be completed.

The reason for discontinuation from the trial will be recorded in the eCRF.

